#### **11.4.4.4    Multiple Comparisons Procedure for Primary Efficacy and Secondary Endpoints**

The overall familywise error rate (FWER) will be controlled at  $\alpha = 0.05$  using the sequential testing procedure for the primary efficacy endpoint comparing between the three dose levels of Ziltivekimab vs. placebo. The high dose (30 mg) will be compared with placebo at the beginning. If significant then the middle dose (15 mg) will be compared with placebo. If the middle dose is significant, then the low dose (7.5 mg) will be compared with placebo. The procedure stops whenever a nonsignificant test occurs.

Secondary endpoints are not included in the multiplicity control.

#### **11.4.5       Safety Analysis**

##### **11.4.5.1    Adverse Events**

The adverse event verbatim descriptions (investigator terms from the CRF) will be classified into medical terminology using the Medical Dictionary for Regulatory Activities (MedDRA). Adverse events will be coded to primary System Organ Class (SOC) and preferred term (PT) using MedDRA, Version 21.0.

Treatment emergent adverse events (TEAEs) are defined as AEs that initiated or worsened on or after the date of first dose of study drug up to the end of safety-follow-up. For AEs occurring on the first dosing day, if the start time cannot be ascertained, the event will be counted as treatment-emergent.

Safety events of special interest (Section 9.3) will be summarized by dose group and treatment assignment.

An overview of AEs will be provided including counts and percentages of subjects with the following:

- Any TEAEs (overall and by maximum severity)
- Any study drug related TEAEs (overall and by maximum severity)
- Any TEAEs of special interest (overall and by maximum severity)
- Any serious AEs (SAEs)
- Any treatment-emergent serious AEs (TESAEs)
- Any TEAEs leading to discontinuation of study drug
- Any TEAEs leading to discontinuation of study
- Any AEs leading to death
- Any severe hematologic AEs (see [Section 11.4.5.7](#))
- Any severe non-hematologic AEs

The number and percentage of patients reporting TEAEs and SAEs for each preferred term will be tabulated by system-organ class, by system- organ class and severity, and by system-organ class and relationship to Study Drug. If more than one event occurred with the same preferred term for the same patient, the patient will be counted only once for that preferred term using the most severe or related occurrence for the summary by severity, or relationship to study drug, respectively.

Listings will be presented specifically for SAEs and TEAEs leading to discontinuation of study drug.

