## **2 STUDY GOAL AND OBJECTIVES**

Patients with NDD-CKD, who have evidence of systemic inflammation with increased cardiovascular risk, will be enrolled into this trial. The purpose of this trial is to determine a dose to select for a potential cardiovascular outcome trial with Ziltivekimab. The current trial will determine which dose of Ziltivekimab will have a significant reduction in hs-CRP with acceptable increases in LDL-C or triglycerides and without clinically meaningful reductions in neutrophils and platelet counts. Doses to be tested will be 7.5 mg, 15 mg and 30 mg subcutaneous monthly compared to placebo for six months.

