### **3.1.2 Safety Endpoints**

- Proportion of patients with AEs, SAEs, severe hematologic AEs, severe non-hematologic AEs, and AEs leading to discontinuation.
- Proportion of subjects with thrombolysis in myocardial infarction (TIMI) major bleeding event.
- Description and frequency of events of special interest by treatment group:
  - Serious infections.
  - Severe injection-related reactions.
  - Gastrointestinal perforations.
  - Hypersensitivity reaction during study drug administration.
  - Anaphylaxis occurring at any time, even if considered unrelated to the study drug. A CRF for the collection of the details of such reactions will be available in the electronic data capture (EDC) system.
  - Neutrophil  $<500/\text{mm}^3$  (severe) or neutrophil  $<1000/\text{mm}^3$  (severe) with evidence of concurrent infection. These events will be separately summarized by treatment group and dose.
  - Thrombocytopenia (platelet count  $<50,000/\text{mm}^3$  [severe]) or platelet count  $<75,000/\text{mm}^3$  (moderate) with evidence of concurrent TIMI major bleeding. These events will be separately summarized by treatment group and dose.
  - Malignancies

- Description of additional safety assessments by treatment group and dose: vital signs, electrocardiogram (ECG), clinical laboratory, and anti-drug antibodies (binding and neutralizing).

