#### **4.5 Temporary Discontinuation of Study Intervention**

Participants may have their study drug administration temporarily suspended during the course of the study. Study drug administration should be temporarily withheld if the participant experiences one or more of the following:

- ALT >3x ULN (moderate)
- Neutrophils <1000/mm^3 (severe)
- Platelet count <50,000/mm^3 (severe)
- Platelet count <75,000/mm^3 (moderate) with evidence of concurrent TIMI major bleeding.

Laboratory measures should be present on two independent assessments. After a temporary suspension of study drug has been performed, study drug may be restarted provided the participant has met the following criteria:

- Neutrophils  $\geq 1500/\text{mm}^3$ , and
- Platelets  $\geq 100,000/\text{mm}^3$

No ongoing clinical sequelae attributable to neutropenia or thrombocytopenia, respectively. If, after restarting study drug, the event causing temporary discontinuation reoccurs study drug should be discontinued permanently.

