#### 11.4.5.2    Laboratory Tests

Laboratory values (excluding efficacy laboratory parameters) will be summarized by treatment group, including changes from baseline at each visit.

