#### 11.4.5.7 Bleeding Events

Bleeding events will be classified using the TIMI Bleeding Classification in [Table 8](#).

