**Table 8 TIMI Bleeding Classification**

Parameter	Criteria
Major	Intracranial hemorrhage or a $\geq 5$ g/dl decrease in the hemoglobin concentration or a $\geq 15\%$ absolute decrease in the hematocrit
Minor	Observed blood loss: $\geq 3$ g/dl decrease in the hemoglobin concentration or $\geq 10\%$ decrease in the hematocrit. No observed blood loss: $\geq 4$ g/dl decrease in the hemoglobin concentration or $\geq 12\%$ decrease in the hematocrit
Minimal	Any clinically overt sign of hemorrhage (including imaging) that is associated with a $<3$ g/dl decrease in the hemoglobin concentration or $<9\%$ decrease in the hematocrit
All TIMI definitions take into account blood transfusions, so that hemoglobin and hematocrit values are adjusted by 1 g/dl or 3%, respectively, for each unit of blood transfused. Therefore, the true change in hemoglobin or hematocrit if there has been an intervening transfusion between two blood measurements is calculated as follows: $\Delta$ Hemoglobin = [baseline Hgb – post-transfusion Hgb] + [number of transfused units]; $\Delta$ Hematocrit = [baseline Hct – post-transfusion Hct] + [number of transfused units $\times$ 3].	
TIMI = Thrombolysis In Myocardial Infarction. Source: Rao 2006	

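### The safety endpoint severe hematologic AEs is tied by cross-reference to a bleeding-only classification, so it and its non-hematologic counterpart lack a valid definition

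*Protocol*

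**What the plan says.** Protocol Section 3.1.2 lists as safety endpoints the proportions of patients with "severe hematologic AEs, severe non-hematologic AEs, and AEs leading to discontinuation". A separate bullet there lists the proportion with a TIMI major bleeding event.

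Section 11.4.5.1 carries these into the adverse event overview. The hematologic row reads "Any severe hematologic AEs (see [Section 11.4.5.7"). The non-hematologic row has no reference.

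The section pointed to consists of one sentence, "Bleeding events will be classified using the TIMI Bleeding Classification in" Table 8, and that table. Its three classes rest on hemorrhage and on falls in hemoglobin or hematocrit. The lowest class, for example, begins "Any clinically overt sign of hemorrhage (including imaging) that is associated with a" small fall. The protocol gives no other definition of a severe hematologic AE.

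Section 2 makes the counts relevant to the trial's purpose: the dose sought is one with an hs-CRP reduction, acceptable lipid changes, and "without clinically meaningful reductions in neutrophils and platelet counts".

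**The concern.** Two stated safety endpoints depend on where the line between hematologic and non-hematologic is drawn, and the only line the protocol draws is a bleeding scale. A programmer who follows the reference would build a hematologic row of bleeding events and would have no instruction for neutropenia, thrombocytopenia or severe anemia.

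This matters more here than in many trials. Section 3.7 expects the drug class to lower neutrophils and possibly cause neutropenia, and Section 2 makes neutrophil and platelet reductions part of dose selection. A row labelled severe hematologic would naturally be read as evidence on that question, arm by arm, and would not contain it.

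**Working it through.** No figure in the protocol has to be reproduced. The check follows the reference and then every other route by which a severe cytopenia could be counted.

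**Step 1. Does the reference work as a definition?**

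| What the row needs | What Section 11.4.5.7 and Table 8 provide |
|---|---|
| A severe grade | Major, Minor, Minimal |
| Hematologic events | Hemorrhage, hemoglobin and hematocrit falls only |
| Neutrophil criterion | None |
| Platelet criterion | None |

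If only Major is taken as severe, the row repeats the TIMI major bleeding endpoint of Section 3.1.2. If all three classes are taken, it also counts minor and minimal bleeds, which the table does not call severe. Neither reading gives a distinct endpoint, and neither yields a usable complement for the non-hematologic row.

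**Step 2. Where else are severe cytopenias counted?**

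- *Events of special interest (Sections 3.1.2 and 9.3).* These cover neutrophils <500/mm3, or <1000/mm3 with infection; and platelets <50,000/mm3, or <75,000/mm3 with TIMI major bleeding. They are summarized by treatment group and dose and have their own row in the same overview.
- *Adverse event tables (Section 11.4.5.1).* Any cytopenia reported as an adverse event appears by system organ class, preferred term and severity.
- *Laboratory summaries (Section 11.4.5.2).* Values "will be summarized by treatment group, including changes from baseline at each visit". Section 11.3.1 adds SD, quartiles, minimum and maximum.

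**Step 3. What do these routes leave out?**

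Section 4.5 uses the label "Neutrophils <1000/mm 3 (severe") with no infection condition. Set against Section 9.3:

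| Count | Labelled severe in Section 4.5 | Event of special interest |
|---|---|---|
| Platelets <50,000 | Yes | Yes |
| Neutrophils <500 | Yes | Yes |
| Neutrophils 500–999, infection | Yes | Yes |
| Neutrophils 500–999, no infection | Yes | **No** |

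For the last line, a count confirmed on two assessments leads to study drug being withheld (Section 4.5), and an abnormality that interrupts treatment is recordable as an adverse event (Section 9.1). That chain does not operate in two situations. A single unconfirmed count need not lead to a hold. Counts first seen at Weeks 23, 24, 28 or 32 (Sections 5.3.9 and 5.4) come after the last dose at Week 21 and cannot interrupt dosing. Absent symptoms or an intervention, recording then depends on the investigator judging the value clinically significantly worse (Sections 9.1 and 9.6). The non-numeric Table 5 sets the severity grade.

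**The case against.** The strongest reply is that this is an editorial slip with little consequence. The text says see, not defined as. Table 5 defines severe for both adverse events and laboratory values, and events are coded by system organ class, so an experienced team would put neutropenia in the hematologic row whatever the pointer says. Another stale reference supports this: Section 11.3.3 cites Section 4.4 for study completion, which is defined in Section 4.8. This may well explain how the error arose. It does not supply a definition, and the printed reference still contradicts the separate listing in Section 3.1.2.

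Three stronger readings are tempting, and the documents do not support them.

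- *Severe neutropenia and thrombocytopenia go uncounted, or are counted as non-hematologic.* The routes in step 2 count most of them, and every platelet value labelled severe is an event of special interest. Nothing assigns cytopenias to the non-hematologic row; that is only what follows if hematologic is taken to mean Section 11.4.5.7.
- *Visit summaries would hide a few deep falls behind a small mean change.* Suppose 6 of 60 patients fall to 0.9 ×10^9/L and the other 54 do not change. With an assumed common baseline of 4.0, the mean change is 6/60 × (0.9 − 4.0) = −0.31. At the entry floor of 2.0 it is 6/60 × (0.9 − 2.0) = −0.11. The SD of change is 3.1 × √(0.1 × 0.9) = 0.93, or 1.1 × √(0.1 × 0.9) = 0.33, and the minimum is 0.9 in both cases. A uniform fall with the same mean has SD 0 and a minimum of 3.69 or 1.89. The planned statistics tell the two apart, although they do not give the number of patients below a threshold.
- *The lack of a laboratory threshold table, when vital signs and ECG have one, is an error.* Such tables are commonly left to the SAP, which is not at hand.

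It is also fair that Section 2 speaks of reductions in counts and does not name the severe hematologic row as the measure of them.

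**Conclusion.** The cross-reference is wrong as printed. It leaves two safety endpoints, severe hematologic and severe non-hematologic AEs, without a valid definition, and it makes the first overlap TIMI major bleeding. This should be corrected. The effect is on the labelling and content of two overview rows; no efficacy analysis is touched.

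The evidence on cytopenias is largely intact. The only count that the protocol labels severe and that can escape event-level reporting is neutrophils 500–999/mm3 without infection, when unconfirmed or first seen after the last dose. How many patients that involves cannot be estimated from the protocol.

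The conclusion assumes the reference is meant to say what the row contains. A SAP may define the term properly; the protocol's pointer would still need correcting.

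**What to change.** In Section 11.4.5.1:

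1. Remove the reference to Section 11.4.5.7 from the severe hematologic row.
2. Define severe hematologic AEs as adverse events graded severe (Section 9.5, Table 5) that are hematologic by MedDRA coding, including cytopenias at the values the protocol already labels severe: neutrophils <1000/mm3 and platelets <50,000/mm3. Keep the coding element, because a definition by these two counts alone would drop other events such as severe anemia. State that it covers events entered as a diagnosis and as a laboratory finding, since Section 9.1 allows both.
3. Define severe non-hematologic AEs as all other severe AEs.
4. Report the TIMI classification only as its own endpoint, as Section 3.1.2 already lists it.

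Optionally, add a count by dose of patients whose worst post-baseline value crosses either of the two limits. This may sit in the SAP. It is the only part that would show low counts never reported as adverse events.

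The cost is a few sentences and, if wanted, one table from hematology data already collected. No hold or restart rule changes. The small downside is that the severe hematologic rate may look less favourable.

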#### 11.4.5.2    Laboratory Tests

Laboratory values (excluding efficacy laboratory parameters) will be summarized by treatment group, including changes from baseline at each visit.

#### 11.4.5.3    Vital Signs

Vital signs and change from baseline in vital signs will be summarized descriptively at each visit by treatment group. The number and percentage of patients with exceeding pre-defined absolute and relative threshold values will be summarized according to [Table 6](#).

When calculating the percentages for the criterion related to a threshold, the numerator will be the number of subjects with normal baseline with respect to the specific criterion and at least 1 post-baseline outlier value within the analysis period; and the denominator will be the number of subjects with a baseline and at least 1 post-baseline assessment within the analysis period.

**Table 6 Pre-defined Threshold Value for Vital Signs**

Parameter	Criteria
Systolic Blood Pressure (SBP)	>25% mmHg increased or decreased from baseline
SBP	>160 mmHg
SBP	<90 mmHg
Heart Rate (HR)	>100 beats per minute
HR	<50 beats per minute
Respiration Rate	>24 breaths per minute
BMI	>10% increased from baseline
BMI	>10% decreased from baseline

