### **Medical Conditions or Diseases**

8. Expected to require blood transfusion within 12-weeks post-randomization.
9. Thromboembolic event within 12-weeks prior to randomization.
10. Clinical evidence or suspicion of active infection.
11. History of peptic ulcer disease or gastrointestinal ulceration in the 12-months prior to randomization.
12. History of active diverticulitis in the 12-months prior to randomization.
13. History of inflammatory bowel disease that has been clinically active during the 12-months prior to randomization.
14. Uncontrolled hypertension (defined as an average SBP  $>160 \text{ mmHg}$  or an average diastolic blood pressure (DBP)  $>100 \text{ mmHg}$  during screening. Patients may be re-evaluated within 2 weeks, at the discretion of the investigator for this criterion if anti-hypertensive therapy has been started or increased as a result of initial screening blood pressure being above these limits.
15. Planned coronary revascularization (PCI or CABG) or any other major surgical procedure.

16. Major cardiac surgical, non-cardiac surgical or major endoscopic procedure within the past 6 months prior to Randomization.
17. History of New York Heart Association Class IV congestive heart failure within 12-weeks prior to randomization.
18. Actively treated or active malignancy during the 1-year prior to randomization with the exception of successfully treated nonmetastatic basal cell or squamous cell carcinomas of the skin and/or local carcinoma in situ of the cervix.
19. History of bone marrow or solid organ transplant or anticipated to receive an organ transplant during the time frame of the study.
20. Known allergy to the study drug or any of its ingredients.

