### 11.1 Sample Size

The primary efficacy endpoint is percent change from baseline in hs-CRP (average of the hs-CRP value prior to randomization and Day 1) to Week 13 between each active group and placebo. Based on the observed treatment difference in percent change from baseline in hs-CRP of -60.74% between combined COR-001-01 active groups and placebo and the associated pooled SD of 16.893% in hs-CRP at Week 4 from the final analysis of study COR-001-SC1, a sample size of 54 per group yields more than 99% power with 2-sided alpha=0.05. Taking into consideration the dropout rate of 10% by the end of the study, a sample size of 60 per group is planned for this study

Approximately 240 patients (60 per group) will be randomized.

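### Table 6 gives its systolic change criterion in a unit that can be read two ways and pools rises with falls, so the count is ambiguous and never shows direction

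*Protocol*

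**What the plan says.** Section 11.4.5.3 says of the vital signs: "The number and percentage of patients with exceeding pre-defined absolute and relative threshold values will be summarized according to" Table 6. A patient counts for a criterion if the baseline was normal for it and there is "at least 1 post-baseline outlier value within the analysis period".

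Table 6 has three systolic rows: above 160 mmHg, below 90 mmHg, and one change row, ">25% mmHg increased or decreased from baseline". For BMI it has two change rows, ">10% increased from baseline" and ">10% decreased from baseline". Table 7 (ECG) also names a direction in its QTcF change rows, which count increases only, in msec.

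The same section provides a second display: "Vital signs and change from baseline in vital signs will be summarized descriptively at each visit by treatment group".

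**The concern.** There are two faults in one row.

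- **Unit.** A percent sign followed by mmHg defines no quantity. The programmer must choose 25% or 25 mmHg. The section's lead-in does not settle it, since it announces both absolute and relative thresholds.
- **Direction.** A patient whose pressure rose sharply and one whose pressure fell sharply add to the same number. If a drug moves pressure one way, it adds patients at one end and removes them at the other, and the two can offset.

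At stake is how this safety count is read, arm by arm, in a trial meant to choose a dose for a possible cardiovascular outcome trial (protocol section 2). No endpoint, test or stopping rule uses the row.

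**Working it through.** The protocol states no expected count for Table 6, so there is no figure of its own to reproduce. It also gives no systolic mean or SD. The values marked as assumed below are assumptions.

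**Inputs from the protocol**
- Systolic ceiling at entry: screening average not above 160 mmHg (exclusion 14).
- Post-baseline visits with vital signs, from the visit lists in sections 5.3 and 5.4: Weeks 4, 5, 9, 13, 17, 21, 23, 24, 28 and 32, which is ten.
- Patients per arm: 60 (section 11.1).

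**Step 1: what the two units mean.** The relative limit in mmHg is 0.25 × baseline.

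| Baseline (mmHg) | 25% of baseline (mmHg) |
|---|---|
| 100 | 25 |
| 130 | 32.5 |
| 140 | 35 |
| 160 | 40 |

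Above a baseline of 100 mmHg, the 25 mmHg reading is always the easier one to meet.

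**Step 2: one visit, closed form.** For a change with mean 0 and SD s, P(|change| > c) = 2Φ(−c/s). Take s = 15 mmHg (assumed).
- 25 mmHg reading: 2Φ(−25/15) = 0.0956.
- 25% at baseline 120 (c = 30): 0.0455. Ratio 0.0956/0.0455 = 2.1.
- 25% at baseline 140 (c = 35): 0.0196. Ratio 0.0956/0.0196 = 4.9.
- 25% at baseline 100 (c = 25): ratio 1.0.

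**Step 3: any of ten visits, simulated.** Assumed: true systolic mean 136, between-patient SD 13, visit-to-visit SD 10 mmHg, one baseline reading kept at or below 160. Percentage of patients with at least one change above 25%:

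| True shift (mmHg) | Rise | Fall | Pooled row |
|---|---|---|---|
| 0 | 10.3 | 3.3 | 13.6 |
| −5 | 5.1 | 8.5 | 13.6 |
| +5 | | | 19.0 |
| −10 | | | 20.9 |
| +10 | | | 29.5 |

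Repeat simulations differ by a few tenths of a percentage point. The near-cancellation at −5 also appears at a visit SD of 8 (4.0% to 3.5%) and of 12 (28.0% to 29.0%). It arises for a fall and not for a rise because, with no effect, rises outnumber falls: a low baseline reading tends to be followed by higher ones, and 25% of a low baseline is fewer mmHg.

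A second set of assumptions (mean 135, between-patient SD 12, visit SD 10, ten visits, baseline between 95 and 160), expressed per 60 patients:

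| Reading | Shift (mmHg) | Rise | Fall | Pooled |
|---|---|---|---|---|
| 25% | 0 | 5.9 | 2.0 | 7.9 |
| 25% | −5 | 3.0 | 5.2 | 8.1 |
| 25 mmHg | 0 | 12.6 | 10.7 | 23.2 |
| 25 mmHg | −5 | 6.5 | 19.0 | 25.4 |

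A few patients have both a large rise and a large fall, so the parts can slightly exceed the pooled figure. Under either reading the pooled row moves little while the falls about double (19.0/10.7 = 1.8) or more (5.2/2.0 = 2.6).

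**Step 4: size of the unit effect, no drug effect.** With the first set of assumptions the pooled count is 38.7% for 25 mmHg against 13.6% for 25%, a factor of 38.7/13.6 = 2.8. The factor is 2.1 to 4.3 for visit SDs of 12 down to 8. Over a wider grid (mean 125 to 145, visit SD 8 to 14) it runs from 1.5 to 6.5 for any of ten visits and from 1.9 to 6.6 for a single visit.

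**The case against.** The strongest reply is that direction is not lost. Change from baseline is summarised by visit and arm, where a mean shift of 5 mmHg appears with its sign. The rows above 160 and below 90 are directional as well: in the model of step 3, a 5 mmHg fall takes the first from 22.6% to 12.8% and the second from 1.8% to 4.0%. This stands, and it limits the consequence. It does not fully replace the change row, because a fall from 150 to 105 mmHg (45/150 = 30%) meets neither absolute limit.

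It can also be said that mmHg is probably a leftover and that 25% was meant, since the BMI change rows are percentages, and that the SAP, which is not shown, may settle it. Both are plausible. Neither makes the protocol's row readable as printed, and a SAP would have to depart from or interpret it.

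Two stronger readings are tempting. A reader might infer that the pooled row cannot show any hypertensive or hypotensive effect. Step 3 shows otherwise: a rise of 5 mmHg, or a shift of 10 either way, moves the total. A reader might also infer that the absence of a diastolic row is an error, since exclusion 14 sets a diastolic limit. Nothing in the protocol promises such a row, an eligibility limit does not require one, and diastolic change is already within the by-visit summaries.

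**Conclusion.** The point holds as an error in one row. The unit is undefined, and the pooling departs from the table's own treatment of BMI without a stated reason. The row never identifies direction and can hide a fall of about 5 mmHg; larger shifts, and rises of 5 mmHg, show in the total. The choice of unit alters the count by an amount that depends on the systolic distribution: about 2 to 4 fold for visit SDs of 12 to 8 mmHg, about 1.5 to 6.6 over the wider assumed range, and not at all at a baseline of 100 mmHg. A flat factor of 2 to 4 would claim more than the protocol supports, as it gives no systolic mean or SD. The consequence is confined to one descriptive safety count, so this is a minor point, worth correcting because the correction is so cheap.

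**What to change.** State a single unit for the systolic change criterion, percent or mmHg; the unit and the cut-off are for the sponsor to set. Replace the one row with two, systolic increase from baseline and systolic decrease from baseline, as Table 6 already does for BMI. Carry the same wording into the SAP and the table shells before the 13-week unblinding. The cost is a table edit and one more output line. No new data or visits are needed, and no diastolic rows are requested.
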